2 BACKGROUND AND RATIONALE

EPU's provide care for women experiencing abdominal pain, vaginal bleeding, or seeking reassurance following previous pregnancy loss. These units aim not only to offer accurate diagnosis of early pregnancy outcomes by determining the location and viability of the pregnancy, but also aim to reassure women, provide emotional support, and counsel for possible outcomes. Miscarriage, occurring in 1 in 5 pregnancies, is defined by the Royal College of Obstetricians and Gynaecologists (RCOG) as pregnancy loss before 24 weeks and early pregnancy loss as before 13 weeks. (1,4–6)

Miscarriage Prediction Models

In recent years, several miscarriage prediction models have been created to aid in counselling and guide decisions regarding further early pregnancy ultrasound scans. Whilst some of these models have been validated, the understanding of their impact on psychological well-being and patient acceptability is not well understood.

Our retrospective study of 5,427 pregnancies demonstrated that our miscarriage prediction model which included maternal factors (ethnicity, smoking, age, bleeding history) alongside ultrasound markers significantly improved predictive accuracy (AUC = 0.88, CI 0.87–0.80). (7) A strength of this model, is the data for these maternal factors are routinely collected. However, prospective validation is required. Before conducting a large validation study (~1,800 patients), it is crucial to first assess whether the model improves psychological well-being and is acceptable to patients.

Psychological impact of early prediction models

Early pregnancy loss, including miscarriage and ectopic pregnancy, frequently causes profound psychological distress, with around 20% of women reporting moderate depression, 18–32% experiencing anxiety, and 25–39% showing symptoms of post-traumatic stress

disorder (PTSD) within 4–6 weeks of the loss.(8) While these rates typically resolve to baseline levels within a year, the psychological toll in the immediate aftermath can be significant.(8)

Threatened miscarriage, defined as vaginal bleeding with a closed cervix and no fetal loss, is also associated with heightened levels of depression and anxiety.(9) This raises important questions about the role of prediction models in mitigating or exacerbating such distress.

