A transvaginal ultrasound scan will be performed by a Gynaecologists who is specifically trained in early pregnancy ultrasound. The purpose of the transvaginal ultrasound scan includes determining the location of pregnancy, the viability and where appropriate recording of number of embryos. This is done with measurement of CRL, FHR, GSD and YSD. Pregnancy dating is based on CRL of a live embryo. In pregnancies < 7 weeks the greatest length of the embryo is taken as the CRL as crown and rump are not clearly visualised. Beyond 7 weeks, the CRL is measured in sagittal section of the embryo whilst excluding the yolk sac. The fetal heart rate is calculated as beats per minute using the software of the ultrasound machine after measurement with electronic calipers of the distance between two heart waves on a frozen M-mode image. The GSD is calculated as the average of three perpendicular diameter with the calipers placed at the inner edges of the trophoblast. The YSD is calculated as the average of three perpendicular diameter with the calipers placed at the center of the yolk sac wall. This is all part of routine clinical care.

At the end of their appointment, participants will be asked to complete a baseline HADs score. The HADs score is a widely used screening tool used to assess psychological distress, including anxiety and depression in clinic settings. It is a self-rating patient reported outcome measure. Fourteen items are divided equally in two subscales for anxiety (HADS-A) and for depression (HADS-B). The ratings of the 14 items are summed to give a final score ranging from 0 to 42. The HADs score has been used frequently in pregnant populations.

The PSWQ is a 16-item self-report scale which is designed to measure the trait of worry in adults.

The patients will be asked how they would like to be contacted in 7 days to repeat the HADS and PSWQ score. We will enquire if they consent to being contacted via email, telephone or text message.

Women will be randomly allocated to either receive their miscarriage prediction score or to the control group who do not receive any intervention. Randomisation will be carried out by the means of a computer-generated random numbers. To prevent selection bias, allocation will be concealed, and a secure online system (REDCap) will assign patients automatically.

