For the patients allocated to intervention, the clinician will then calculate their score but inputting the patient's data on to a excel spreadsheet which will calculate the patient miscarriage prediction score using the following equation:

$$Y = -2.382 + 0.052 \times \text{maternal age (years with decimals)} + 0.482 \text{ if Afro-Caribbean} - 0.341 \text{ if South Asian} + 0.393 \text{ if East Asian} - 0.073 \text{ if Mixed ethnic origin} + 0.213 \text{ if Parous} + 0.647 \text{ if Smoker} - 0.165 \text{ if Abdominal pain as indication of the scan} + 0.709 \text{ if Vaginal bleeding as indication of the scan} + 0.239 \text{ if previous miscarriage as indication of the scan} - 0.226 \text{ if previous ectopic pregnancy as indication of the scan} - 0.241 \times \text{CRL (mm)} - 0.036 \times \text{delta FHR (bpm)} - 0.178 \times \text{delta Gestational sac diameter (mm)} + 0.633 \times \text{delta Yolk sac diameter (mm)} - 0.005 \times (\text{CRL} \times \text{delta GSD}) + 0.038 \times (\text{CRL} \times \text{delta YSD}) - 0.003 (\text{delta FHR} \times \text{delta GSD}) + 0.104 \times (\text{delta GSD} \times \text{delta YSD})$$

The patients randomized to intervention will then receive their score on the same day and could choose to do so either face to face or over the telephone. The General Practitioner will be informed of the patient's participation in the study.

For both groups 7 days after their initial assessment a repeat HADS and PSWQ score will be performed. This will be sent to the patient as previously consented. The patient will be sent two questions about the acceptability of the

1. Did receiving the miscarriage prediction score help you feel more informed and prepared about your pregnancy outcome? *(Yes/No, with an optional text box for further explanation.)*
2. Would you recommend that other women in early pregnancy receive a miscarriage prediction score as part of their care? *(Yes/No, with an optional explanation.)*

The primary outcome will be the difference in HADS and PSWQ at 7 days between cases and controls.

A power calculation was conducted to determine the required sample size for assessing the psychological impact of providing an individual with their miscarriage prediction score at the time of assessment. Given the non-parametric nature of Hospital Anxiety and Depression (HADS) scores, the Wilcoxon Mann-Whitney rank sum test was chosen.

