5 STUDY SCHEDULE

Screening (Day 0)

- Record demographics and ultrasound findings in the Viewpoint clinical records
- 2D transvaginal ultrasound scan
- Verify eligibility based on inclusion/exclusion criteria.
- Provide information leaflet and verbal explanations
- Obtain and document consent from potential participant on screening consent form.
- Allocate a study number and record the patient's MRN / NHS number in the site file (paper)
- Use of the prediction model to calculate risk of miscarriage (study excel spreadsheet on NHS Onedrive)
- Randomisation into intervention or control group. If intervention, to be given miscarriage prediction score.
- Patients to complete HADS and PSWQ score
- Consent patient how they would like to be contacted for follow up

Repeat testing (Day 7)

- 7 days after initial assessment the patient will be sent follow up HADS, PSWQ score and acceptability questions.
- If patient does not complete score on this day, a reminder will be sent as per patients contact requests.

Table 1: Schedule of Assessments

	Screening	7 Days
Visit No	1	2
Window of flexibility for timing of visits:	+/- 2 days	+/- 2 days
Informed Consent	X	
Medical History	X	
2D TVUS	X	
Eligibility confirmation	X	
HADS/PSWQ Score	X	X
Acceptability Questions		X
Randomisation	X	
Adverse Events Review		X

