7 ELIGIBILITY CRITERIA

7.1 Inclusion Criteria

In order to be eligible to participate in this study, an individual must meet all of the following criteria:

- Have capacity to understand the study and to provide signed and dated informed consent.
- Willing to comply with all study procedures and be available for the duration of the study including consenting to follow up of the pregnancy outcome by letter, phone or email according to individual preference.
- Age 16 years or over
- Single live ongoing intrauterine pregnancy less than 12 weeks gestation

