12 DATA HANDLING AND MANAGEMENT

Clinical and research data for this study will be initially recorded in the electronic patient record (EPR) and the PIA Viewpoint Database at King's College Hospital. This system forms the source data and includes ultrasound findings and clinical notes recorded during the participant's visit.

Electronic data, including demographic and outcome measures (HADS and PSWQ scores), will be exported in pseudonymised form to a password-protected Microsoft Excel file and stored securely on the NHS OneDrive. Hard copies of consent forms and screening logs will be stored in a locked clinical office at the Early Pregnancy and Acute Gynaecology Unit.

Data will not be transferred to any external institutions. All data handling and analysis will be conducted within the research team at King's College Hospital. Only delegated members of the study team will have access to pseudonymised datasets, and no identifiable data will be shared.

Confidentiality will be strictly maintained in line with NHS information governance standards. All data will be pseudonymised using unique participant study IDs, and no names or NHS numbers will be used in the exported research datasets.

No formal data monitoring committee is required due to the minimal risk, non-interventional nature of the study. The Principal Investigator and Chief Investigator will act as data custodians and will oversee all aspects of data collection, quality control, and storage.

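### The day-7 questionnaires, and the reminder to women who have not completed them, go out with no check of the unit's own records for a pregnancy loss

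*Protocol*

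**What the plan says.** Protocol section 4 applies the repeat measurement to both arms without condition: "For both groups 7 days after their initial assessment a repeat HADS and PSWQ score will be performed". Section 5 (Day 7) gives the dispatch rule: "7 days after initial assessment the patient will be sent follow up HADS, PSWQ score and acceptability questions". It continues: "If patient does not complete score on this day, a reminder will be sent as per patients contact requests".

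Section 4 sets out the two acceptability questions in a single version. The first is: "Did receiving the miscarriage prediction score help you feel more informed and prepared about your pregnancy outcome".

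On the state of women after a loss, section 2 says that "the psychological toll in the immediate aftermath can be significant". On where clinical information is held, section 12 says that data are "initially recorded in the electronic patient record (EPR) and the PIA Viewpoint Database".

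**The concern.** The trial enrols women with a live pregnancy who are at risk of miscarriage, and some will miscarry within the week. Where the unit already holds a record of that loss, the written procedure still sends the standard form. An intervention-arm woman is then asked whether her score prepared her for the outcome, and she is reminded if she does not answer that day. The protocol acknowledges that this is a time of marked distress, and section 15.3 names distress attributable to study procedures as a ground for pausing or stopping. It builds no safeguard into the one procedure that predictably meets these women.

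Two things are at stake. The first is avoidable distress caused by the trial itself. The second is less certain. Day-7 HADS and PSWQ are the primary outcome, so if women with a loss answer less often because the contact is ill-suited to them, missing data would depend on the very event that the score predicts.

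Rules for contacting participants are trial conduct and belong in the protocol. They are not something that a statistical analysis plan would supply.

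**Working it through.** **1. Is any step conditional on pregnancy status?**

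| Step | Who receives it | Condition on pregnancy status |
|---|---|---|
| Day-7 HADS and PSWQ (sections 4 and 5) | Both arms | None |
| Acceptability questions (sections 4 and 5) | Every woman, one wording | None |
| Reminder (section 5) | Only women who have not completed the form; one reminder, by the route each woman chose | None |

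**2. Does another provision supply the check?**

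- Section 7.1 requires "consenting to follow up of the pregnancy outcome by letter, phone or email according to individual preference". No timing is given, and nothing links this to the day-7 contact.
- Table 1 lists an adverse events review at day 7, but it is not described as happening before the form is sent.
- Section 6 allows withdrawal at any time, which leaves the woman to act.
- Section 15.3 allows suspension for distress, which acts only after the event.

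None of these is a check before contact. Section 12 shows that the records needed for one are held in systems that the team already uses.

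**3. How many women?** The documents give no rate of loss within 7 days of a scan showing a heartbeat. Section 2 gives only an overall figure of 1 in 5 pregnancies. I therefore assume 1% to 5%; this range is mine and has no source in the protocol.

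Expected number = women randomised × 7-day loss rate.

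- With the stated total of 372: 372 × 0.01 = 3.7 and 372 × 0.05 = 18.6.
- The 372 includes an allowance for 75% acceptance, so fewer may be randomised. The unadjusted 208, inflated only for 20% dropout, gives 208 / 0.80 = 260. Then 260 × 0.01 = 2.6 and 260 × 0.05 = 13.0.
- Chance of at least one such woman, treating losses as independent, at the least favourable corner: 1 − 0.99^260 = 0.927. With 372 women at 1% it is 1 − 0.99^372 = 0.976.

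The 372 serves here only as a denominator. It does not follow from the stated allowances: 104 / (0.80 × 0.75) = 173.3, so 174 per group and not 186. That is a separate matter. Any total between 260 and 372 gives counts within the limits above.

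**4. What cannot be computed.** The documents do not allow an estimate of how many of these losses would be on the unit's records by day 7, or how many of the women would also be non-completers and so receive the reminder.

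**The case against.** The strongest reply is that section 5 describes an ordinary follow-up step and does not forbid looking at the records first. The covering message, reminder text and information sheet are not shown, so nobody can say that they are insensitive. The day-7 adverse events review and the pregnancy-outcome follow-up are natural places for a check. This stands in part. The unseen wording cannot be criticised, and I do not criticise it. But the dispatch rule and the first acceptability question are visible, and as written the rule needs no check.

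A reader might infer more than the documents support:

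- *That every woman is reminded, or that bereaved women are routinely chased.* The text provides one reminder, to non-completers only, by an agreed route.
- *That all of them are asked about a score they were given.* This fits the intervention arm only. Women in the other arm are a "control group who do not receive any intervention", although the text sends them the same questions.
- *That the prediction equation in section 4 gives the rate.* Its output is not a 7-day risk and would overstate the size.
- *That non-response bias is established.* No passage shows that women with a loss reply less often, or that the wording would cause it.
- *That the acceptability items should be reworded after a loss.* This would change a secondary outcome on a post-randomisation event, and would lose comparability among women for whom the question is highly relevant.

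The remedy also has a cost of its own. The covering message before a self-reported outcome would depend on a post-randomisation event in an unblinded trial. Recording of losses could differ by arm if receiving the score affects whether women return to the unit. That objection stands, and the fix has to make it visible.

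**Conclusion.** The point holds as a gap in trial conduct that should be closed. The day-7 contact and the reminder to non-completers are unconditional, and no other provision acts as a check beforehand. On an assumed 7-day loss rate of 1% to 5%, about 4 to 19 of 372 women, or 3 to 13 of 260, would have a loss when the form is due. At least one such woman is about 93% likely or more across that range. Only those with a loss on the unit's records would be reached by a check, and that number is unknown.

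The case rests on participant protection. The effect on missing data is plausible but unquantified. Sample size, power and significance level are untouched.

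**What to change.** Add to section 5 (Day 7): before the form is sent, and again before any reminder, a member of the study team checks the electronic patient record and Viewpoint for a recorded pregnancy loss. Where one is found, the team uses a sensitive covering message and reminder wording approved by the Research Ethics Committee, and records the loss and its date.

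Keep HADS, PSWQ and both acceptability items unchanged, in the same window and by the same rule in both arms. The check changes how a woman is approached, not whether she is followed up or analysed. A pregnancy-status question on the form could not replace it, because it is read only once the form has arrived.

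Costs: a sentence or two in section 5, one alternative message and reminder for ethics approval, and a short record check per woman, repeated before a reminder. Losses managed elsewhere will be missed. Because the covering message would vary with a post-randomisation event whose recording could differ between arms, report by arm how many women received it.

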6 CONSENT

Informed consent will be obtained from all. Participants will be provided with a written Participant Information Sheet (PIS) that explains the study purpose, procedures, potential risks, and benefits in clear, non-technical language. This will be supplemented by a verbal explanation given by a member of the research team, with ample opportunity for the participant to ask questions.

Written consent will be obtained using a study-specific Informed Consent Form (ICF), which will be signed and dated by the participant and the person obtaining consent. A copy of the signed form will be provided to the participant, and the original will be securely filed in the study records.

Consent will be recorded in the participant's clinical notes and in the site file. Only individuals with delegated authority and appropriate GCP training will obtain consent.

This study will include only participants who are able to speak and understand English, as the psychological tools used (HADS and PSWQ) have not been validated in translation and the prediction model requires clear explanation to ensure understanding. Therefore, non-English speakers are excluded. Vulnerable populations, such as those undergoing psychiatric treatment, are also excluded for ethical and clinical reasons.

Participants will be informed that participation is voluntary and that they may withdraw from the study at any time without affecting their standard medical care.

7 ELIGIBILITY CRITERIA

7.1 Inclusion Criteria

In order to be eligible to participate in this study, an individual must meet all of the following criteria:

- Have capacity to understand the study and to provide signed and dated informed consent.
- Willing to comply with all study procedures and be available for the duration of the study including consenting to follow up of the pregnancy outcome by letter, phone or email according to individual preference.
- Age 16 years or over
- Single live ongoing intrauterine pregnancy less than 12 weeks gestation

7.2 Exclusion Criteria

An individual who meets any of the following criteria will be excluded from participation in this study:

- Women with pregnancies of unknown location, ectopic pregnancies or early pregnancy prior to an embryo being seen or an embryo without a heartbeat.
- Multiple pregnancies
- Those undergoing assessment or treatment for a psychological condition by a psychiatrist
- Those who do not speak English or require a translator
- Women who have taken part in another clinical trial in the last 3 months.

8 RECRUITMENT

Eligible participants will be recruited from the Early Pregnancy and Acute Gynaecology Unit at King's College Hospital. Recruitment will occur during routine clinical appointments for women undergoing early pregnancy ultrasound scans.

Recruitment Schedule:

Recruitment is planned to begin in April 2026 and will continue over a 12 month period until the required sample size of 372 participants is achieved.

Identification and Approach:

Patients presenting with a single live intrauterine pregnancy at less than 12 weeks' gestation will be identified by the clinical team as part of routine care. A delegated member of the research team will approach eligible patients after their clinical scan, explain the study, and provide the Participant Information Sheet (PIS).

9 STATISTICAL METHODS

Sample Size Derivation:

The planned sample size was calculated to detect a clinically meaningful difference in psychological distress scores (HADS and PSWQ) between the intervention and control groups. Based on prior studies, a non-parametric Wilcoxon Mann-Whitney rank sum test was selected due to the expected distribution of psychological score data.

Calculation Method:

The study was powered at 80% to detect a probability shift of 0.362 with a two-sided significance level of 0.05. Accounting for a 75% consent rate and 20% attrition, the adjusted total sample size is 372 participants (186 per arm). Statistical support was provided by

internal collaborators, and calculations were cross-verified using standard power analysis tables.

Justification for Design and Analysis Plan:

A randomised controlled trial (RCT) design was selected to allow unbiased assessment of the psychological impact of providing a miscarriage prediction score. The use of validated psychometric tools (HADS and PSWQ) permits a robust and reproducible outcome assessment. Analysis will compare between-group changes in scores from baseline to 7 days post-assessment.

Baseline Data Summary:

Demographic and clinical data, including maternal age, ethnicity, parity, smoking status, and presenting symptoms, will be summarised at baseline using descriptive statistics. Comparability of groups at baseline will be assessed.

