PI	Principal Investigator
PIS	Participant Information Sheet
PSWQ	Penn State Worry Questionnaire
QA	Quality Assurance
QC	Quality Control
REC	Research Ethics Committee
SAE	Serious Adverse Event
SDV	Source Data Verification
SOP	Standard Operating Procedure
TMF	Trial Master File
YSD	Yolk Sac

STUDY SUMMARY

STUDY OVERVIEW	
Full title	The Psychological Effects of Miscarriage Prediction Score: A Prospective Study
Objectives	Primary: Assess psychological effects of the miscarriage prediction model. Secondary: Evaluate patient acceptability.
Type of trial	A randomised, single-site trial in pregnant women with ongoing intrauterine pregnancies <12 weeks.
Trial design and methods	Prospective, non-blinded RCT at a single centre. HADS and PSWQ used to assess psychological impact at baseline and day 7.
Health condition(s) or problem(s) studied	Threatened miscarriage, psychological impact in early pregnancy.
Target sample size	372 participants (186 per arm, adjusted for consent/dropout).
Trial duration per participant:	7 days (from consent to follow-up psychological questionnaire).
Main inclusion/exclusion criteria:	Inclusion: Pregnant women >16 years with ongoing singleton intrauterine pregnancy <12 weeks. Exclusion: Non-English speakers, psychiatric treatment, multiple pregnancies, or planned terminations.
Statistical methodology and analysis:	Non-parametric Wilcoxon Mann-Whitney rank sum test. Powered at 80% to detect difference in psychological outcomes. Sample size estimated based on expected variance in HADS scores.
STUDY TIMELINES	
Study Duration/length	1 year
Expected Start Date	April 2026
End of Study definition and anticipated date	Final follow-up of last enrolled participant.
Key Study milestones	IRAS submission, ethics approval, first participant enrolment, data collection completion.
STORAGE of SAMPLES	
Data collected / Storage	PIA Viewpoint Database (King's College Hospital). Anonymised data stored securely on NHS OneDrive.

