The study was calculated to have 80% power and to detect a probability shift of 0.362 with a 0.05 two-sided significance level. We estimated a 75% acceptance level and 20% dropout rate. Based on these parameters, an initial required sample size was calculated to be 104 participants per group, giving a total of 208 participants. After the adjustments for dropout rates and consent rates, this would equate to 186 participants per group and a total of 372 participants.

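### The primary comparison is the day-7 score in section 4 but change from baseline in section 9, and the protocol does not say which one the rank-sum test or the 0.362 applies to

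*Protocol*

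**What the plan says.** Section 4 (Study Design) defines the outcome: "The primary outcome will be the difference in HADS and PSWQ at 7 days between cases and controls". Section 9 (Statistical Methods) describes the analysis: "Analysis will compare between-group changes in scores from baseline to 7 days post-assessment".

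One test is named. The Study Summary gives "Non-parametric Wilcoxon Mann-Whitney rank sum test. Powered at 80% to detect difference in psychological outcomes". Section 9 says "a non-parametric Wilcoxon Mann-Whitney rank sum test was selected due to the expected distribution of psychological score data", in the paragraph on sample size. The section 9 sentence on changes names no test.

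The sample size in section 4 is set to "detect a probability shift of 0.362 with a 0.05 two-sided significance level" at 80% power, giving "104 participants per group, giving a total of 208 participants" before inflation to 186 per arm. It does not say whether 0.362 describes day-7 scores or changes.

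HADS and PSWQ are scheduled at both visits (section 5, Table 1). Section 4 describes the baseline HADS before it describes allocation. The day-0 list in section 5 puts the questionnaires after randomisation and after the intervention arm has been given the score.

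**The concern.** A day-7 score and a change from baseline have different variances and can give different p-values on the same data. A reader cannot tell which comparison is primary, or which one the sample size was meant to support.

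This matters more than usual here. The trial is not blinded, all analysis is done within the research team (section 12), there is no data monitoring committee, and section 15.3 foresees an interim data review. Two candidate primary analyses leave room for a choice made after data have been seen, even an unintended one.

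The two also differ in power, in a direction that depends on a correlation the protocol does not state. A third option, the day-7 score adjusted for baseline, uses data already being collected and is usually more precise than either.

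**Working it through.** **The plan's own figure.** Noether's formula for the rank-sum test with equal arms is N = (z₀.₉₇₅ + z₀.₈₀)² / (3(p − 0.5)²). With p = 0.362, N = 7.849 / (3 × 0.138²) = 137.4, or 69 per arm. The stated 104 per arm is not reproduced; it matches p of about 0.388, a shift of about 0.4 SD for normal scores. That mismatch is a separate matter. It means the calculation cannot show which variable was intended. The check below takes 104 per arm as given, with a 0.4 SD effect, at which the day-7 rank-sum test has about 80% power.

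**Large-sample variances.** Let r be the correlation between baseline and day 7, with equal SDs at both times. Relative to the unadjusted day-7 score (1), change has variance 2(1 − r) and the linear baseline-adjusted day-7 score has 1 − r². The number per arm giving the same power as 104 on day-7 scores is:

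| r (assumed) | Change: 104 × 2(1 − r) | Adjusted: 104 × (1 − r²) |
|---|---|---|
| 0.3 | 145.6 → 146 | 94.6 → 95 |
| 0.5 | 104 | 78 |
| 0.7 | 62.4 → 63 | 53.0 → 54 |

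Change is less precise than the day-7 score when r is below 0.5 and more precise when it is above.

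**Simulation, normal scores** (104 per arm, 0.4 SD, 3000 runs per case):

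| r | Day-7 rank-sum | Change rank-sum | ANCOVA on day 7 |
|---|---|---|---|
| 0.3 | 81% | 68% | 87% |
| 0.5 | 80% | 80% | 91% |
| 0.7 | 80% | 95% | 98% |

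**Simulation, skewed scores.** The variance formulas belong to linear models, and the protocol chose a rank test because of the expected score distribution. With right-skewed, rounded scores on 0 to 42 (lognormal, median 6, log-SD 0.8; an assumption), the day-7 rank-sum test stays at about 80%. Raw-score ANCOVA with robust standard errors gives 76% at latent correlation 0.4, 82% at 0.5 and 91% at 0.7. At correlations of 0.3 to 0.4 it runs at 75% to 78%, slightly below the simple rank-sum test.

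**Across normal and skewed scores, correlations 0.3 to 0.7:** change-score rank-sum has about 56% to 95% power; rank-based baseline-adjusted analysis has about 84% to 97% and exceeded both stated analyses in every case run. The low end for change scores comes from skewed scores at correlation 0.3.

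**If baseline follows disclosure.** Let disclosure shift the baseline score by a fraction f of its day-7 effect. The linear adjusted estimate keeps 1 − r·f of the effect, and the change score keeps 1 − f. With f = 1, adjustment keeps 70%, 50% or 30% at r = 0.3, 0.5 or 0.7, and change keeps nothing. Baseline adjustment is therefore sound only if baseline comes first.

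**The case against.** Covariate adjustment is commonly left to the SAP, which is not at hand, so its absence from the protocol is not an error. That stands: adjustment is recommended here as the better way to settle the definition. It does not excuse the contradiction, because the protocol itself states both versions.

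Several stronger readings are tempting and are not supported.

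- **That the plan wastes the baseline.** This is true only on the section 4 reading. Under section 9 the baseline enters through the change score, though inefficiently.
- **That baseline adjustment can never do worse, so that 104 per arm would be worth about 139 (104/0.75 at r = 0.5) under either stated analysis.** This rests on linear-model variances with equal SDs. Raw-score ANCOVA fell slightly below the rank-sum test with skewed scores at low correlation.
- **That the rank-sum test is explicitly prescribed for both variables.** It is the only test named, but the sentence on changes names none.
- **That adjusting for baseline resolves everything.** It does so only if baseline is taken before disclosure, and on this the order in section 5 conflicts with that in section 4. The section 5 list may not be meant as a strict sequence, but nothing says so.

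It is also fair to say that change scores do better than unadjusted day-7 scores when the correlation is above 0.5 and scores are near normal. The protocol gives no correlation from which to argue this.

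**Conclusion.** The contradiction is certain, since it lies in the protocol's own text. The protocol should be corrected before data are analysed.

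Its size is less certain. It rests on an assumed correlation of 0.3 to 0.7, assumed score distributions, and 104 evaluable participants per arm with an effect that gives the day-7 rank-sum test about 80% power. Under those assumptions, reading section 9 literally could lower power to about 56% or raise it to about 95%. The advantage of rank-based adjustment over both readings was consistent in the cases run, but its size cannot be fixed from the protocol.

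A reader might infer that the ambiguity will be exploited, or that settling it also settles the primary endpoint. The documents show only that there is room for a choice. Whether HADS and PSWQ are both primary, and how they share the error rate, is a separate question that this point leaves open.

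**What to change.** 1. Use one definition in the Study Summary, section 4 and section 9: the day-7 score compared between randomised arms. Delete the change-score sentence or mark it as descriptive.
2. State that 0.362 refers to the day-7 score. If the sponsor finds that it was derived for changes, redo the calculation for the day-7 score.
3. Reconcile sections 4 and 5 so that baseline HADS and PSWQ are completed before randomisation and before any score is disclosed.
4. Subject to item 3, adjust the primary comparison for the baseline score by a rank-based or ordinal method, for example rank ANCOVA or a proportional-odds model with baseline as covariate. Keep the unadjusted rank-sum test on day-7 scores as a sensitivity analysis; it also keeps the result on the probability scale of the sample size.
5. State the roles of HADS and PSWQ separately.

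The cost is a protocol amendment, a check of what 0.362 refers to, a defined order for the day-0 steps, and a few lines of analysis code. No new data are needed, since both questionnaires are already scheduled at both visits.
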